## 1.0 Objectives / Specific Aims

Advances in mHealth technology and the ubiquity of smart phone access (~65% of adults in SC have a smart phone: ~75 % of youth older >12yrs) provide a viable approach for improved patient-provider interactions (8-17). Co-Investigator [name], collaborated with The Technology Applications Center for Healthful Lifestyles (TACHL) to develop the Smartphone Asthma Monitoring System (SAMS) with funding from a SCTR pilot award (UL TR000062) to transform post discharge phone call into a mobile technology platform. This monitor system will be repurposed and evaluated in an adult population with COPD, hence the renaming of **Smartphone Airway Monitoring System (SAMS 3.0)**. Numerous studies have demonstrated that exposures to environmental “cues” are associated with respiratory exacerbations, including locations (e.g., exposure to high allergen content –roaches in unkempt houses, etc.), situations (e.g. exercise, stress exposure), negative affective states and environmental context (e.g., time of day, after school outdoor activity). TACHL, in collaboration with various research teams funded by Verizon, Macey & Kellogg Foundations, Duke Endowment, and NIH, has successfully developed several smartphone-enabled biofunction monitoring, medical regimen adherence, and ecological momentary assessment (EMA) systems to assess an individual's emotional state, physical symptoms, functional status, and exposure to relevant environmental triggers (e.g., stress, physical exertion). The relay of self-reported information, biofunction data, and regimen adherence data in conjunction with GPS location tracking of use and associated pollen and pollution counts makes it possible to give a valuable report to a clinician to interact in real time with the patient. These interactions can be automated based on the guidelines (e.g., American Thoracic Society guidelines for COPD) and provider preference and/or live with the use of our evolving telemedicine infrastructure.

Further development of this mHealth solution (SAMS), in combination with a training regimen for the first time, will make this innovative approach to chronic respiratory disease more cost effective and sustainable over time (less personnel required). Preliminary work has been completed at MUSC to develop the SAM system and incorporate objective real-time measurement of medication use with self-report and Bluetooth enabled smart inhalers, EMA probe questions, and COPD follow up questions.

**Testing the feasibility and acceptability of adding a low-risk respiratory strength training regimen, including review of video captured training session, to the current version of SAMS is one goal of the current proposal.** Ultimately our goal is to improve disease control and reduce the frequency of acute care visits for COPD in our state.

**Specific Aim 1:** To evaluate the feasibility and optimize the acceptability, feasibility, adherence, and performance of technology-enhanced self-management and training regimen through quantitative data (e.g. medication adherence, peak flow, and activity monitoring) in males and females with COPD.

**Specific Aim 2:** To assess preliminary signs of efficacy of RESP-FIT with respect to PImax, PEmax, dyspnea, fatigue and self-efficacy. If successful, this intervention will provide participants with the tools to self-manage dyspnea in their homes, thus impacting fatigue and physical activity.

**Specific Aim 3:** To integrate the current version of SAMS (e.g. Ecological Momentary Assessment, recent discharge follow-up questions, training progress via Bluetooth devices or manual entry, video capture of training technique including feedback and smartphone delivered telehealth visits) with adults with COPD.

**Exploratory Aim 4.** To determine if reducing dyspnea, increasing self-efficacy, and decreasing fatigue (i.e., goals of aim 2) results in increased physical activity and improved sleep as measured by activity trackers.

**Primary hypotheses to be tested:** Our overarching hypothesis is that a training regimen consisting of RMST along with technology-enhanced symptom-tracking will decrease dyspnea, dyspnea-related activity avoidance, and fatigue. Additionally, this application proposes to further develop SAMS which currently integrates EMA probe questions covering COPD symptoms and preventive care use with the

new functions, use in an adult population with COPD, video captured training technique and logging of RMST training sessions. Up to thirty adults with COPD (age over 40) will complete the study and use the SAMS app for 6 weeks in the natural environment (**Figure 1**). We will evaluate the acceptability, feasibility, adherence, perception of privacy, and performance of RESP-FIT + SAMS through quantitative methods to further optimize the app and related study procedures for the next phase of testing (i.e., large scale efficacy RCT).

**Figure 1.** Respiratory Fitness (RESP-FIT) and Smart Phone Airway Monitoring System (SAMS) application architecture schematic depicted with encrypted data transfer showing interactions with patients and researchers

## 2.0 Background

**SIGNIFICANCE – Importance of the Problem:** Dyspnea and fatigue are prominent comorbidities of chronic obstructive pulmonary disease (COPD), the third leading cause of death in the United States (CDC, 2016). Both dyspnea and fatigue are associated with exercise intolerance, activity avoidance, and functional impairment, which combine to reduce quality of life in those with COPD (Al-shair et al., 2016). We propose to evaluate an intervention that targets fatigue and dyspnea through a novel respiratory muscle strength training (RMST) and physical fitness self-management program, (RESP-FIT), specifically designed to strengthen inspiratory and expiratory muscles, promote physical activity engagement, and improve quality of life in persons with COPD.

The aversive potential of respiratory restriction in COPD is devastating, leaving many patients in continual fear of suffocation. They learn to fear restrictive respiratory sensations such as dyspnea, and thus actively avoid engaging in daily activities, including exercise or physical activity (PA) that exacerbate these sensations. This negative cycle of dyspnea-activity aversion frequently results in activity avoidance, physical deconditioning, fatigue, and an overall reduced quality of life (Miller, 2014; Thomas, Decramer, O'Donnell, 2013; von Leupoldt & Janssens, 2016). Self-management interventions containing supervised exercise are effective in COPD (Jordan et al., 2015), but there remains an urgent need for evidence-based interventions to address the physical deconditioning cycle and subsequently improve self-management of dyspnea and fatigue.

**Respiratory muscle strength training (RMST).** RMST is an empirically-validated therapy for improving ventilation and airway defense in a range of non-patient (adolescents, healthy adults, healthy elderly) and patient populations. Among those who have been studied are patients with various degenerative conditions, including neurological and respiratory diseases associated with weakened or damaged respiratory musculature (Luciaga et al., 2014). Respiratory muscle strength trainers (Figure 1) are small, portable, and easy to use. Through application of a pressure threshold, that must be surpassed in

order to inhale or exhale through the device, respiratory muscles are forced into a state of “overload” wherein contractile forces are increased and, over time, respiratory muscle strength and coordination increases. These increases are able to be measured by sampling maximal inspiratory and expiratory pressures (PImax, PEmax) via a hand-held manometer. Our previous pilot work demonstrates increased PImax in patients with COPD following IMST, with improved dyspnea and load compensation (the ability to overcome respiratory resistance) (Martin and Davenport, 2011; unpublished work in review). However, effects of RMST improved dyspnea on fatigue in COPD are unknown.

### 3.0 Intervention to be studied

**RESP-FIT.** The RESP-FIT program is a 6-week respiratory muscle strength training intervention adapted from previous RMST training regimens (Sapienza, Troche, Pitts & Davenport, 2011; Martin & Davenport, 2011; Hegland et al., 2016), consisting of 1) five training days/week using a combined IMST/EMST training device to which we will add Bluetooth enabled frequency and pressure intensity feedback monitoring to determine adherence and precise timing for device threshold intensification (i.e., increasing resistance training) 2) individualized, progress-based text message training reminders and prompts related to timing and intensification calibration, and 3) use of a Fitbit for remote monitoring of physical activity and hours slept at night. The training device is calibrated at 70% of each individual’s baseline PImax and PEmax. Similar to other muscle strength training programs, exercises are done at regular intervals during the week (5 breaths, 5 times a day, 5 days a week; the participant will receive graphical illustration of RESP-FIT training frequency and intensity achieved, and based on their training regimen, will be prompted and/or reinforced via SMS text messaging. Note, this feedback system allows personalized, calibrated, and efficiently timed adjustments of resistance training intensity as respiratory muscle strength improves, rather than simply increasing levels weekly. As the use of an accelerometer or remote tracking device alone may affect physical activity, a control group will receive only the Fitbit. **This study proposes to assess the initial efficacy of RMST by obtaining estimates of variability in fatigue secondary to dyspnea, using a technologically-enhanced RESP-FIT intervention.**

**RESP-FIT Training:** Participants will be trained on a combined expiratory-inspiratory (EMST/IMST) muscle strength training device. The EMST/IMST device is a blue-tooth enabled, adjustable pressure respiratory muscle trainer (with a 22 mm OD adapter) capable of providing a pressure threshold resistance to both exhalation and inhalation on a continuous scale between 1.5 to 20 cm H2O pressure. For each participant, the valve will be set at 75% maximum pressure threshold. In the event that the participant cannot tolerate this pressure threshold, the valve setting will be lowered by 2 cm H2O (to a minimum pressure threshold of 6 cm H2O pressure) until tolerance is achieved. Participants unable to tolerate a maximum pressure threshold of 6 cm H2O will be discontinued from the EMST/IMST device and, after rest, begin use of a low-no resistance device (described below). Participants will be instructed to inhale through the nose and exhale slowly and as deeply as possible through the EMST/IMST trainer 6 times. Participants unable to exhale only through the device will be instructed to pinch their nose closed during exhalation. The number of breaths and pressure setting will be set based on prior clinical experience with the EMST/IMST device, found to provide the greatest effect on dyspnea in patients with COPD. The relationship between exhaled tidal volume, exhaled peak airflow and pressure in the EMST/IMST device was measured previously on a custom manufactured lung simulator for 50 breaths. At an average exhaled tidal volume of  $643 \pm 17$  ml with a peak expiratory flow of  $61.6 \pm 12.1$  l/min, the pressure inside the RMST device was  $13.8 \pm .6$  cm H2O when the device was set at 10 cm H2O. A Resironics Pflex® (model # HS553) inspiratory muscle trainer will serve as the low-no resistance device for this investigation. The Pflex® is designed as a resistive trainer for exhalation and inhalation and features an adjustable orifice through which air is inhaled or exhaled. The diameter of this orifice can be progressively decreased, from a setting of “1” (least resistance to exhalation/inhalation) to “6” (most resistance to exhalation/inhalation). However, for the purposes of this investigation, the Pflex® will be physically altered so as to prevent the device from supplying resistance to exhalation or inhalation. Specifically, each Pflex® will be set at largest opening, position 1. Additionally, a 3mm hole will be drilled into the device body to further reduce the resistance to airflow. Participants will be instructed to inhale through the nose and exhale slowly and as deeply as possible through the low-no resistance device 6 times. Participants unable to exhale only through the devices will be instructed to pinch their nose closed

during exhalation. As with the RMST device, the relationship between exhaled tidal volume, exhaled peak airflow, and pressure in the low-no resistance device was previously measured with a lung simulator for 50 breaths. At an average tidal volume of  $650 \pm 10$  ml, with a peak expiratory flow of  $59.5 \pm 12.9$  l/min, the pressure developed inside the modified low-no resistance Pflex® device was  $2.2 \pm 1.7$  cm H2O.

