**Randomization and Training Regimen:** Following collection of pre-training baseline measures, participants will be randomly assigned 50/50 to either a Standard of Care (SOC) Control Group (n=15), or a SOC + EMST/IMST Group (n=15). Participant randomization will be stratified by gender and dyspnea grade as measured on the MMRC. Those participants assigned to the SOC control group will receive a Fitbit monitoring device, but no intervention beyond that which is typically provided to patients seen within the MUSC Clinic. Participants randomly assigned to receive SOC+EMST/IMST will receive six weeks of clinician-guided, scripted RMST. This training will be facilitated by the PI using a custom-designed and constructed EMST/IMST trainer. Non-invasive measurement of maximum expiratory and inspiratory pressures (PEmax and PImax; described previously) will be obtained in order to set pressure threshold of the EMST/RMST device. The first week of EMST/IMST training will be conducted with the device set at 75% of the average initial PEmax collected at pre-training baseline. After a nose clip is placed the participants will be taught a four-step procedure: 1) take a breath in, 2) wrap lips tightly around the EMST/IMST trainer mouthpiece, and 3) exhale quickly and forcefully until you hear the popping or whistling sound of the device valve opening, and 4) continue blowing forcefully for two seconds. Once the participant is able to do a five-breath trial, another five-breath trial will be completed with the participant allowed as much independence as appropriate. The participant will receive a text message each day reminding them to complete his or her training and "remain active today." Participants in the SOC group will receive a text message reminding them to "remain active today." The daily training session will be as follows: 1) five sets of five-breath exhalations (25 breaths total) completed each training day, 2) each exhalation within a set will be separated by approximately one minute, and 3) each five-breath training set will be separated by five minutes. A Bluetooth-enabled "use" button on the EMST/IMST device will log the times the participant has used their training device. Each participant will be provided with a diary to record five sets of five-breath training trials on five days each week. Our experience indicates that EMST/IMST takes approximately 20 minutes each day. PEmax will be reassessed weekly, by the research clinician across the six-week treatment period and readjusted to 75% of the participant's current PEmax. If no changes in PEmax are observed week to week, treatment

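### The dose rule (70–75% of the participant's own maximum pressure) cannot be set on the stated 1.5–20 cm H2O trainer once PEmax exceeds 26.7 cm H2O (75% rule) or PImax or PEmax exceeds 28.6 (70% rule), and no rule covers a target above 20

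*Combined protocol and SAP*

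**What the plan says.** Section 3.0, under RESP-FIT Training, describes the combined trainer as "capable of providing a pressure threshold resistance to both exhalation and inhalation on a continuous scale between 1.5 to 20 cm H 2 O pressure". The protocol then gives four bases for the setting:

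- Section 3.0, RESP-FIT paragraph: "The training device is calibrated at 70% of each individual’s baseline PImax and PEmax".
- Section 3.0, RESP-FIT Training: "For each participant, the valve will be set at 75% maximum pressure threshold". Whether the maximum is the participant's or the device's is not stated.
- Section 3.0, RESP-FIT Training, later in the paragraph: "The number of breaths and pressure setting will be set based on prior clinical experience with the EMST/IMST device".
- Section 10.0, Randomization and Training Regimen: the first week is "conducted with the device set at 75% of the average initial PEmax collected at pre-training baseline", after which "PEmax will be reassessed weekly, by the research clinician across the six-week treatment period and readjusted to 75% of the" participant's current value.

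Three rules allow a departure from target. An intolerable setting is lowered in 2 cm H2O steps to no less than 6. A participant who cannot tolerate 6 moves to the low-no resistance device. The load is not raised if PEmax has not changed. The Objective Measures table records MIP and MEP in cm H2O, the same unit as the device scale.

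The technique and the device also differ between sections. Section 3.0 has participants "inhale through the nose and exhale slowly and as deeply as possible through the EMST/IMST trainer 6 times". Section 10.0 asks for five sets of five fast, forceful exhalations with a nose clip, and says: "This training will be facilitated by the PI using a custom-designed and constructed EMST/IMST trainer". It gives no pressure range for that trainer. Section 15.0 names the breathing device as the Pflex, which section 3.0 makes the low-no resistance device. Section 18.0 says all supplies can be bought commercially.

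**The concern.** A setting defined as a percentage of the participant's own maximum has no upper bound except that maximum, whereas a device with a stated range has a fixed one. Where the two meet, the protocol needs a rule, and it has none. The three departure rules deal with intolerance and with unchanged strength; none deals with a calculated target above 20 cm H2O. The inclusion and exclusion criteria set no limit on PImax or PEmax.

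Two things are at stake. First, section 12.0 places treatment fidelity among the primary analyses, and fidelity in intensity needs one stated intensity to be measured against. Second, PImax and PEmax change are Aim 2 outcomes, analysed as secondary. For a participant above the ceiling, reporting those changes as the response to training at 70–75% of maximum would misstate the dose, by an amount that depends on that participant's pressures. The study is meant to shape a larger efficacy trial, which would inherit the misdescription. No powered comparison is at risk, because the Sample Size paragraph disclaims one.

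**Working it through.** **Inputs from the protocol.** Device upper limit 20 cm H2O (section 3.0, RESP-FIT Training). Setting fractions 0.70 (section 3.0, RESP-FIT) and 0.75 (section 10.0, Randomization and Training Regimen). The protocol states no ceiling of its own to reproduce.

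**Step 1: highest pressure at which each rule can be set.** Ceiling = device limit / fraction.

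- 75% of PEmax: 20/0.75 = 26.7 cm H2O.
- 70% of PImax or PEmax: 20/0.70 = 28.6 cm H2O.

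**Step 2: size of the gap above the ceiling.** The protocol gives no expected PImax or PEmax, so the PEmax values below are assumptions chosen to show the range. All figures are nominal settings in cm H2O.

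| Assumed PEmax | 75% target | Above 20 by | 70% target | Above 20 by | Top setting as % of PEmax (20/PEmax) |
|---|---|---|---|---|---|
| 25 | 18.75 | 0 | 17.5 | 0 | 80% |
| 30 | 22.5 | 2.5 | 21 | 1 | 67% |
| 40 | 30 | 10 | 28 | 8 | 50% |
| 60 | 45 | 25 | 42 | 22 | 33% |
| 80 | 60 | 40 | 56 | 36 | 25% |
| 100 | 75 | 55 | 70 | 50 | 20% |

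**Step 3: crossing the ceiling during training.** A participant who starts below it can pass it at a weekly reset. From an assumed baseline PEmax of 25, the 75% ceiling is reached after a gain of 26.67/25 − 1 = 6.7%. From 20, it is reached after 26.67/20 − 1 = 33%.

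**Step 4: the alternative reading of section 3.0.** If the 75% there refers to the device maximum, the setting is 0.75 × 20 = 15 cm H2O for everyone, which is within range. That equals 75% of PEmax only when PEmax is 15/0.75 = 20, and 70% only when it is 15/0.70 = 21.4. At other values it is a different dose from the participant-based rules.

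**What is not computed.** Section 3.0 reports one bench test, with 13.8 cm H2O inside the device at a setting of 10. That does not show what pressure a setting of 20 would deliver, so no ceiling on delivered pressure is claimed.

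**The case against.** The strongest reply is that the conflict joins two descriptions that may not concern the same device. Section 3.0 can work alone: a fixed 15 cm H2O with steps down for intolerance. Section 10.0 speaks of a custom-built trainer whose range is not given and may be wider. The protocol also gives no expected pressures, so it shows a conflict of wording and not under-dosing. Both points stand as limits on the claim. They do not remove it. Both sections use the EMST/IMST name, 1.5–20 is the only range given for it, and the 70% rule tied to the participant's own maximum is itself in section 3.0. If the custom trainer has a wider range, the device description is what needs correcting.

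Second, section 12.0 does not define fidelity as a percentage of maximum. The measure it names is training frequency, and sections 3.0 and 12.0 plan pressure monitoring and feedback on the intensity achieved. Staff may therefore notice the limit, and frequency is unaffected by it. But nowhere does the protocol say that the valve setting is recorded, or expressed relative to the participant's maximum.

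Third, this is a pilot, and Section F says information on technology problems will guide refinement of the protocol. That process might catch the limit at first calibration, but it contains no dose rule.

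Fourth, the measurement schedules need not contradict each other. The Objective Measures table (baseline and second visit) and the dependent-variable schedule in section 10.0 (baseline, 3, 6 and 14 weeks) can be read as outcome time points, with weekly PEmax used only to adjust the device. That is a fair reading. Weekly measurement by a clinician still sits badly with section 7.0, where every visit other than the baseline and final ones is held by tablet or phone.

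**Conclusion.** The concern holds. On the stated device, the stated percentage rules cannot be delivered above a PEmax of 26.7 cm H2O (75%) or a PImax or PEmax of 28.6 cm H2O (70%), and no rule says what happens then. This is an error in the text as written, not merely missing detail. Confidence is high in the conflict itself. It does not extend to actual under-dosing: the number of participants affected cannot be derived from the protocol, and would be zero if the trainer's true limit is high enough. The ceilings rest on taking 20 cm H2O as the limit of the trainer used in section 10.0. The consequence is confined to how dose and fidelity are described, which is enough to warrant correction in a study whose primary analyses include fidelity.

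**What to change.** Before enrolment:

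1. Identify the trainer actually used, state its working range, and make sections 3.0, 10.0, 15.0 and 18.0 agree on it.
2. Keep one setting rule throughout: one percentage and one basis, stated for expiration and for inspiration, with one breathing technique and breath count.
3. If 20 cm H2O is the true maximum, define the load as the lower of the target percentage and the device maximum, and do not describe the dose as 70–75% of maximum for participants at the cap.
4. Record the valve setting at each adjustment. Report it as a percentage of the most recent measured PEmax (and PImax where measured), both in the fidelity analysis and beside PImax and PEmax change.
5. State when PEmax is measured during training and, if weekly measurement is kept, how it is done between the on-site visits.

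The cost is protocol wording, one added data field and one derived percentage. No visits are added if PEmax is taken where it is already measured. That choice has a price: under the Objective Measures schedule, with the second visit at Week 6, the reference stays at baseline throughout training and the percentage will drift from the true value as strength changes. Keeping it current requires workable weekly measurement. The stated dose may also look less favourable for participants at the cap.

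### The training load and manoeuvre are prescribed inconsistently, and neither written manoeuvre has the participant inhale against the device in a combined inspiratory and expiratory programme

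*Combined protocol and SAP*

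**What the plan says.** The opening paragraph of Section 3.0 describes a combined inspiratory and expiratory trainer. On load it says "The training device is calibrated at 70% of each" individual's baseline PImax and PEmax. The schedule is "5 breaths, 5 times a day, 5 days a week". Intensity is to be adjusted on device feedback as strength improves, "rather than simply increasing levels weekly".

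RESP-FIT Training, also in Section 3.0, says the device gives "resistance to both exhalation and inhalation on a continuous scale between 1.5 to 20 cm" H2O. It continues "For each participant, the valve will be set at 75% maximum pressure threshold", with step-downs if that is not tolerated. The manoeuvre is: "Participants will be instructed to inhale through the nose and exhale slowly and as deeply as possible through the EMST/IMST trainer 6 times".

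Randomization and Training Regimen, in Section 10.0, says "Non-invasive measurement of maximum expiratory and inspiratory pressures (PEmax and PImax; described previously) will be obtained in order to set pressure threshold", but the only figure it then gives is for expiration: "device set at 75% of the average initial PEmax collected at pre-training baseline". A nose clip is fitted. The participant breathes in, then seals the lips on the mouthpiece, then exhales fast and hard. A training day is five sets of five exhalations. A research clinician rechecks PEmax each week and resets the load to 75% of the current value; if PEmax has not changed, the load is held.

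No section says which of these governs.

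**The concern.** Staff cannot carry out all three descriptions at once. A participant wearing a nose clip cannot inhale through the nose, and a slow exhalation is not a forceful one. The load has two percentages and three reference pressures, one of them undefined.

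The more serious matter is the missing inspiratory step. The programme is described as training both directions, the opening of Section 3.0 sets a load from PImax, and Aim 2 (Section 1.0) names PImax as an outcome. If staff follow either written manoeuvre, a flat PImax result could mean that inspiratory training failed or that it was never given. A rise could not be credited to it either. The regimen taken forward to the larger trial would carry the same ambiguity.

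**Working it through.** **1. The three descriptions side by side**

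| Element | 3.0, opening | 3.0, RESP-FIT Training | 10.0, Training Regimen |
|---|---|---|---|
| Expiratory load | 70% of baseline PEmax | 75% of an undefined maximum | 75% of PEmax, rechecked weekly |
| Inspiratory load | 70% of baseline PImax | not separately stated | PImax measured, no percentage given |
| Breath in | not described | through the nose | nose clip on, before lips seal on mouthpiece |
| Breath out | not described | slow and deep | fast and forceful |
| Count | 5 x 5 x 5 | 6, no sets or days | 5 sets of 5, 5 days a week |
| Progression | timed by feedback, follows strength | step-down for intolerance only | weekly check, follows PEmax |

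**2. Breath count.** Section 10.0's own figure reproduces: 5 sets x 5 exhalations = 25 a day. Over 5 days that is 125 a week, and over 6 weeks 750. The opening of Section 3.0 gives the same. RESP-FIT Training gives 6 with no frequency, so no six-week total can be derived from it.

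**3. Load reference.** If the undefined maximum means the top of the device range, the setting is 0.75 x 20 = 15 cm H2O for everyone. If it means the participant's PEmax, it agrees with Section 10.0. The text does not decide between these.

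**4. Loaded inhalation.** In RESP-FIT Training the inhalation is nasal, so it bypasses the device. In Section 10.0 breathing in is step 1 and sealing the lips is step 2, so the inhalation again comes before contact with the device. The exhalations in a set are about one minute apart, which does not suggest continuous breathing through the trainer. Neither step list loads inspiration.

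**5. PImax remeasurement between baseline and end of training.** Section 10.0, which collects all dependent variables at 3 weeks, implies one. The Objective Measures table, which lists baseline and the second study visit (Week 6, under Participant Compensation), implies none. Neither is tied to a rule for resetting the inspiratory load, whereas PEmax has a weekly one.

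**6. Device range (conditional).** If 20 cm H2O is the true upper setting, the stated load can be set only while percentage x maximal pressure is at most 20:
- at 75%: 20 / 0.75 = 26.7 cm H2O (PEmax);
- at 70%: 20 / 0.70 = 28.6 cm H2O (PEmax or PImax).

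The documents give no PEmax or PImax values, so the number of participants affected is unknown, and the printed range may itself be the error.

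**The case against.** The best defence is that Section 10.0 is the detailed procedure and agrees with the opening of Section 3.0 on the count, so the six-breath text is the outlier and may describe an initial fitting. Training is also described as scripted, so the clinician script may contain the inspiratory step. Weekly technique videos are reviewed by the investigators, and Section 12.0 (Sample Size) says that the pilot is not meant to test effectiveness.

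Most of this stands, and it lowers the severity. It does not remove the point. RESP-FIT Training names no separate fitting phase. Section 10.0 read alone still has no inspiratory percentage, loaded inhalation or PImax reset. Video review needs a stated manoeuvre to check against.

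A reader might infer more than the documents support:
- *That the progression rules contradict each other.* Both follow strength, because Section 10.0 holds the load when PEmax is unchanged. They differ in timing only.
- *That no way of measuring progress is stated.* Section 3.0 names Bluetooth pressure feedback, Section 10.0 a clinician assessor, and Section 2.0 and the Objective Measures table the instruments. What is missing is how weekly PEmax is obtained when Section 7.0 makes the interim visits remote.
- *That no inspiratory load is set at all.* The opening of Section 3.0 does set an initial one.
- *That the primary fidelity analysis fails.* Section 12.0 does not define fidelity as delivered over prescribed load. The measure it specifies is training frequency, on which the opening of Section 3.0 and Section 10.0 agree.
- *That six breaths is a rival six-week dose.* No frequency is attached to it.

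**Conclusion.** The point holds as an inconsistency that should be fixed. The load is given as 70% of PImax and PEmax, 75% of an undefined maximum, or 75% of PEmax. The two written manoeuvres cannot be combined, and neither loads inspiration. PImax has no readjustment rule to match the weekly one for PEmax.

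The harm is to the interpretation of PImax change and to the regimen carried into the next trial. Training frequency, the sample size and the stated precision do not depend on it. The conclusion assumes that staff work from the written steps; if the clinician script already has a loaded inhalation, the fault is only that the protocol omits it. A reader might conclude that the device cannot deliver the prescribed load, but without PEmax or PImax values the documents cannot show that.

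**What to change.** - Make the Section 10.0 procedure, with its 5 x 5 x 5 count, the governing one. Delete the six-breath slow-exhalation text or label it as something else.
- State one percentage and one reference pressure for each direction.
- Add an inhalation through the device against load, or cite the clinician script if it contains one, and reassess PImax whenever PEmax is reassessed. If inspiratory training is not intended, remove the inspiratory-training and PImax-load wording. That clinical choice is the sponsor's.
- State one timing rule for progression and how weekly pressures are obtained between on-site visits.
- Check the 1.5 to 20 cm H2O range against the stated load, and correct whichever is wrong.

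The cost is a protocol amendment, retraining on one script, a brief added PImax measurement, and some extra effort for the 15 trained participants. No additional patients are needed.
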